The objectives of this proposal, accordingly, are to corroborate data from our preliminary human studies showing that a high protein diet results in body weight loss. We will correlate the observed clinical findings with an understanding of normal and pathological appetite regulatory mechanisms in experimental animals. In order to accomplish the stated goals of this program, we have brought together interdisciplinary collaborations at our VA Medical Center from diverse backgrounds including: microbiome, cell biology, molecular biology, neurophysiology and human clinical investigations, including health services research to investigate the mechanisms regulating feeding behavior and obesity. Our proposal is focused on addressing three hypotheses linking clinical and translational approaches that are critical to understanding the pathophysiology of satiety/obesity.

1. A higher protein replacement diet will result in early satiety signaling and weight loss in obese patients and a differential pattern of postprandial GI hormone release.
2. Patients on the high protein diet will have shifts in the composition and function of their intestinal microbiome.
3. Abundance of specific fecal microbes can be used to predict response to a high protein diet.

C. Specific Objectives.

AIM 1: To Confirm the Hypothesis that a High Protein Diet Reduces Body Weight and Alters the Pattern of Postprandial Gut Hormone Release in Obese Patients.

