Rationale: In the first aim, we will evaluate whether an isocaloric high protein diets (1 gram of protein per pound of lean body mass) will improve weight loss in comparison to a standard protein diet based on 0.5 gram of protein per pound of lean body mass. Our preliminary studies support the concept that a higher protein meal replacement will result in significant losses of body mass in obese subjects and that a high endogenous level of ghrelin in patients with neuroendocrine tumors results in increased weight gain. In the study, bioelectrical impedance will be used to determine the protein requirement at the level of 0.5 or 1 gram per pound of lean body mass. Weight loss will be the primary outcome. A secondary variable will include satiation as measured using a standard questionnaire, liver stiffness as determined by transient elastography, and microbiome changes determined by 16S sequencing. In addition, we will establish the changes in the levels of the orexigenic peptide ghrelin including the ratio of ghrelin to des-acyl ghrelin, and anorexigenic peptides PYY, leptin, CCK, GLP-1 and nesfatin-1 following high protein meal ingestion.

AIM 2. Characterize the changes in the fecal microbiome induced by a high protein diet

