i. Ghrelin: Isolated in 1999, ghrelin is an orexigenic peptide hormone secreted mainly by the X/A-like cells of the gastric fundus and is the endogenous ligand of the growth hormone secretagogue receptor (GHS-R).⁽⁴⁶⁾ In humans, plasma ghrelin levels rise prior to meals and fall after eating.⁽⁴⁷⁾ Ghrelin has been implicated in both mealtime hunger and the long-term regulation of body weight. Levels are known to negatively correlate with body mass index (BMI) so that levels are increased in both obese patients who have lost weight through dietary restriction and patients with anorexia nervosa.⁽⁴⁸⁾ Also, patients who have lost weight secondary to gastric bypass surgery have suppressed ghrelin levels. Not only are the levels lower than in those patients who have lost weight by nonsurgical means, but also the meal-related fluctuations and diurnal rhythm are not found after gastric bypass surgery.⁽⁴⁹⁾ There is also a clear negative association between ghrelin and insulin secretion.^(47,50) In the rat as in humans, ghrelin is principally synthesized in X/A-like cells in the oxytic mucosa of the fundus.⁽⁴⁶⁾ The major forms of ghrelin include acylated ghrelin, in which serine-3 is octanoylated (a unique biological finding), and non-acylated ghrelin.⁽³⁾ In blood, non-acylated ghrelin circulates in far greater amounts, accounting for more than 90% of total ghrelin.⁽¹⁰⁾ In rodents, we have shown that the stimulatory action of ghrelin on food intake is linked with the activation of neuropeptide Y (NPY) synthesizing neurons⁽¹⁰⁾ in the arcuate nucleus (Arc) that projects to the paraventricular nucleus of the hypothalamus (PVN) and lateral hypothalamic areas. Both of these hypothalamic nuclei regulate feeding behavior and energy balance. In this way, ghrelin is thought to serve as the missing link between enteric nutrition and central regulation of energy balance.⁽³⁾ Recently we also established that non-acylated ghrelin can counteract the orexigenic action of ghrelin in rats⁽⁵¹⁾ but showed that obestatin, a newly identified ghrelin associated peptide (GAP) that is putatively derived from post-translational processing of the prepro-ghrelin gene, did not influence food intake contrary to the initial claim.⁽⁵²⁾

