4. WORK PROPOSED

A. AIM 1: To Test the Hypothesis that a High Protein Diet Reduces Body Weight and Alters the Pattern of Postprandial Gut Hormone Release in Obese Patients.

Rationale: High protein intake has been associated with reduced caloric intake, and meal replacements are an effective strategy for weight loss and weight maintenance in obese subjects.⁽⁴⁾ The primary objective of this study is to evaluate whether the high protein diets based on 1 gram of protein per pound of lean body mass will improve weight loss in comparison to a standard protein diet based on 0.5 gram of protein per pound of lean body mass. In all arms of the study, bioelectrical impedance will be used to determine the protein requirement at the level of 0.5 or 1 gram per pound of lean body mass. The prescribed calories will be the same on all meal replacement weight loss plans. Weight loss will be the primary outcome. Secondary variables will be satiation as measured using a standard questionnaire, bioelectrical impedance analysis, transient elastography, 16S rRNA sequencing and shotgun metagenomics. A third variable will be multi satiety hormone responses as measured before and after a meal.

The study described below is also unique in its design in that in the same subjects we will assess the changes in gut hormone release and the microbiome (Aims 2 and 3). This is the first study to investigate the effects of meal composition on satiety in connection with the microbiome. The result of this study will guide future clinical trials on weight loss with high protein diet in subjects.

Recruitment: Subjects will be recruited through the use of IRB-approved flyers which will be distributed in the primary care and subspecialty clinics. Online advertisement on ClinicalTrials.gov will also be used to disseminate information about this study to make an outreach effort that spans the entire community. In addition, those patients that are being evaluated as part of our MOVE program, a national weight management program designed by the VA NCP, would be provided with information regarding the study.

Approximately 200 healthy volunteers age 30 years and older between BMI of 27 to 40 kg/m² will be able to take part in this study. Patients must fulfill all of the following conditions or characteristics in order to be considered for study enrollment:

Inclusion criteria:

- a. Age 30 years and older at screening.
- b. BMI of 27 to 40 kg/m² inclusive.

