erect with feet together and head level; height will be measured to the nearest 0.5 cm. Weight will be measured to the nearest 0.25 lbs using a balanced scale. BM will be calculated as weight in kilograms divided by the square of the height in meter. Waist and hip circumferences will be measured in the standing position. The subject should be wearing unrestricting undergarments with a hospital gown being optional. Waist circumference will be measured at the level midway between the lateral lower rib margin and the iliac crest. Hip circumference will be measured at the level of the trochanters through the pubic symphysis.

v. Study Visits: Participants in both groups will meet with registered dietitians every 2 to 4 week throughout the Intervention Phase and the dietary intake patterns will be reviewed. A variety of visual tools including food models and common household measuring utensils will be used during the interview to help participants gauge amounts accurately.

a. Assessment will be performed at weeks 0, 2, 4, 6, 8, 12, 16.

1. Vital signs
2. Height
3. Weight
4. Vital Signs
5. Fasting Labs: CBC/Metabolic Panel, Hemoglobin alc, TSH, Cholesterol, TG, HDL, blood sugar, hormone panel (leptin, CCK, GLP-1, PYY, ghrelin, insulin, nesfatin-1)
6. Body Composition and estimated resting metabolic rate
7. Hepatic transient elastography
8. Stool collection for fecal short chain fatty acids and microbiome analysis
9. Satiety Scale
10. 3-Day food record
11. Food frequency questionnaire
12. Adverse Event Tracking

Compliance with consumption will be assessed using check lists that will be turned in during clinical visits. Minimal accepted compliance will be set at 80% of the assigned diet. A participant will be withdrawn once cumulative consumption levels fall to the point that 100% compliance cannot get them over the 80% threshold by the final day of the intervention.

Study Schedule

Procedures	Screen Week -1	Baseline Week 0	Week 2	Week 4	Week 6	Week 8	Week 12	Week 16
Informed Consent	X							
Medical History	X							
Physical Examination	X							
Labs: Serum Pregnancy Test (if needed)	X							
Urine Pregnancy Test (if needed)	X							
Height		X	X	X	X	X	X	X
Weight		X	X	X	X	X	X	X
Vital Signs		X	X	X	X	X	X	X
Labs: CBC/Metabolic Panel, Hormones,		X	X	X	X	X	X	X

Hemoglobin a1c, TSH, lipids							
Body Composition BIA		X	X	X	X	X	X
Liver Stiffness Fibroscan		X	X	X	X	X	X
Product Dispensing		X	X	X	X	X	X
Stool collection		X	X	X	X	X	X
Satiety Scale		X	X	X	X	X	X

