To assay the levels in hormones that are released in the high protein *versus* standard protein meal, we intend to use the "Obesity Peptide Biomarker Chip" from Phoenix Pharmaceuticals (Appendix 2). From the designed antibodies immobilized on the nitrocellulose coated slide, the results from this assay can qualitatively indicate the concentration of these obesity-related hormones from serum/plasma, adipocytes, or conditioned medium. This kit contains a two-pad glass slide. Each pad has been spotted with 36 to 40 kinds of capture antibodies to detect the corresponding sample antigens. First, the test serum is biotinylated and purified. Following purification, the nonspecific binding sites of the capture antibodies are blocked with blocking

solution. Biotinylated antigens in the sample or in the standard solution can then bind to the capture antibodies immobilized on the nitrocellulose pads. Streptavidin-horseradish peroxidase is added and will subsequently catalyze the chemiluminescence substrate solution. The enzyme-substrate reaction is imaged by CCD camera, chemiluminescence imager, or X-ray film. Spot intensity will be counted and is directly proportional to the amount of antigen in the test sample. A direct comparison between sample and standard will give the biomarker profile in question. After knowing which marker is up or down regulated, the conventional ELISA will be used for accurate quantitation of those biomarkers. We first obtain the baseline of hormone release before starting the meal replacement, at fasting, 1 hour, 2 hour, and 4 hour postprandial time-points. At the first week after initiation of the meal replacement, the subjects repeat the above tests. The test interval is then extended to one month to two months.

ix. Bioelectrical Impedance Analysis (BIA), Hepatic Transient Elastography (Fibroscan) and Anthropomorphic Measurements:

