Secondary Statistical Analyses: All analyses will be performed using SAS software (SAS Institute Inc., Cary, NC). First, linear mixed-effects regression model (or GEE model) will be constructed to examine the study effect on the weight loss over time among the two diet plans, referred to as Model 1. Covariates include gender, diet group (high-protein and standard), time that the measurement is taken, and an interaction between diet plan and time. Models also include the subject-level random effects to account for the correlation between repeated measures at baseline and subsequent follow-up visits occurring at 2 week to 1 month intervals. Next, mixed-effects regression models will be used to evaluate the differences in hormonal patterns among the three diet plans for various hormones of interest (e.g., CCK, GLP-1, etc). Since the hormonal level over time is expected to be nonlinear, the covariates in the model include diet group (normal vs. high-protein), time (in days), and smooth-spline function of time by group interaction. Next, we will also construct linear mixed-effects regression models to examine the study effect on the continuous efficacy variables and safety variables (e.g., vital signs) over time among the three diet plans using PROC MIXED. The continuous efficacy variables include nutritional assessments (FFQ, 3DFR, and Satiety), selected laboratory and biochemical variables (e.g., HbA1c, insulin), body fat, etc. Models include the same fixed effects in Model 1, and the subject-level random effects, which account for the correlation between repeated measures at baseline and pre-defined time points for different variables (e.g.,

baseline and at weeks 2, 4, 6, 8, 12 and 16 for the nutritional assessments). Lastly, generalized linear mixed-effect regressions will be used to model *any* dichotomous and categorical (e.g., severity of adverse events) secondary variables, respectively, in the PROC GLIMMIX or GENMOD. All tests will be two-sided, and significance level is $p < 0.05$.

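### Aim 1 asks about postprandial hormone release, but the stated hormone model has no meal-time term, no postprandial response is defined, and the post-meal draw timing does not match the visit list

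*Combined protocol and SAP*

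**What the plan says.** **Question.** The Aim 1 title (Specific Objectives) says that the diet "Alters the Pattern of Postprandial Gut Hormone Release in Obese Patients". The Aim 1 rationale under Work Proposed adds: "A third variable will be multi satiety hormone responses as measured before and after a meal".

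**Sampling.** Under Hormonal and Biochemical Assays: "We first obtain the baseline of hormone release before starting the meal replacement, at fasting, 1 hour, 2 hour, and 4 hour postprandial time-points". The series is repeated in the first week after meal replacement starts, and after that at intervals of one to two months. Study Visits gives a different calendar: "Assessment will be performed at weeks 0, 2, 4, 6, 8, 12, 16". The assessment list there includes "Fasting Labs: CBC/Metabolic Panel, Hemoglobin alc, TSH, Cholesterol, TG, HDL, blood sugar, hormone panel", with no post-meal draw.

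**Analysis.** Secondary Endpoints names hormones only by their level. Secondary Statistical Analyses specifies mixed-effects models in which "the covariates in the model include diet group (normal vs. high-protein), time (in days), and smooth-spline function of time by group interaction". It gives expected nonlinearity over time as the reason for the spline.

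**Test meal.** The Aim 1 rationale under Specific Objectives refers to ghrelin and "anorexigenic peptides PYY, leptin, CCK, GLP-1 and nesfatin-1 following high protein meal ingestion". The assay section instead contrasts a high protein with a standard protein meal. Neither states what is eaten at the baseline series.

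**The concern.** A postprandial pattern is a within-day curve: where the hormone starts at fasting and how it moves over the next four hours. The only time scale in the stated model is days. Such a model can describe how a hormone's average level drifts over 16 weeks in each arm. It cannot describe how the response to a meal differs between arms.

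Nothing else in the plan fills the gap. No section defines an AUC, a peak or a rise from fasting, or says how the four draws of one day enter the model. The hormone half of Aim 1 could therefore be reported from a contrast that mixes fasting level with meal response. Alternatively, the response measure could be chosen after the data are seen.

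The schedule adds to this. If it is unclear which days carry four draws and which carry a fasting draw only, it is also unclear what each point on the day axis represents.

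**Working it through.** The plan gives no figure for this analysis, so there is none to reproduce. The check asks what the listed covariates can estimate from the planned draws.

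**1. Inputs.** Draw times 0, 1, 2 and 4 h (assay section). Covariates: diet group, time in days, spline of time by group (Secondary Statistical Analyses). Assumption: the draws enter as raw values with time in whole days.

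**2. What the model can separate.** Take 2 arms, 4 test days and 4 draws, giving 2 × 4 × 4 = 32 arm-day-hour cells. The days used were 0, 7, 56 and 112; the later ones are assumed, because the plan does not fix them. Let the day-by-arm part be saturated, which is at least as flexible as any spline in days.

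- Arm and day only: 8 distinct design rows, rank 8. The four draws of an arm-day share one fitted mean.
- Adding meal time and its interactions with arm and day: rank 32. Fasting and post-meal means become separable.

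A subject-level random intercept does not change this, since it is the same for all four draws.

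**3. The diet contrast on a test day.** Let d0 be the between-arm difference at fasting, and let the difference in rise from fasting be r at each of 1, 2 and 4 h. The differences at the four draws are d0, d0 + r, d0 + r and d0 + r. Their mean is

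(4·d0 + 3·r)/4 = d0 + 0.75r.

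- Pure fasting shift (d0 = 1, r = 0): contrast 1, although the meal response is unchanged.
- Pure meal-response difference (d0 = 0, r = 1): contrast 0.75.
- Offsetting case (d0 = 3, r = -4): differences 3, -1, -1, -1; contrast 0.

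**4. The same cases under a postprandial summary.** The trapezoid weights for 0, 1, 2 and 4 h are 0.5, 1, 1.5 and 1. After the fasting value is subtracted, net incremental AUC differs by r(1 + 1.5 + 1) = 3.5r.

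| d0 | r | Pooled contrast | Mean rise from fasting | Net incremental AUC |
|---|---|---|---|---|
| 1 | 0 | 1 | 0 | 0 |
| 0 | 1 | 0.75 | 1 | 3.5 |
| 3 | -4 | 0 | -4 | -14 |

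Either summary separates the two sources; the pooled contrast does not.

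**5. A second illustration, with invented values.** Arm A is 10, 10, 10, 10 and arm B is 7, 13, 11, 9 at the four draws. Both average 10, so the day-only model fits a diet difference of 0. Incremental AUC is 0 in A. In B the rises are 6, 4 and 2, giving 1·6 + 1.5·4 + 1·2 = 14.

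**6. Timing, side by side.**

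| | Hormonal and Biochemical Assays | Study Visits |
|---|---|---|
| Baseline | fasting, 1, 2, 4 h | panel under fasting labs |
| Week 1 | series repeated | no visit |
| Later | every one to two months, no weeks named | weeks 2, 4, 6, 8, 12, 16; panel under fasting labs |

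The assay section gives an outline, but it does not map onto the calendar.

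**The case against.** The strongest reply is that this is under-specification and not a wrong model. The word *include* need not introduce a complete list. Days could be recorded as fractions. The dependent variable could be a per-day response, since Aim 1 speaks of responses before and after a meal. All of this is possible, but none of it is written. Fractional days would help little without further specification: one hour is 1/24, about 0.04 of a day, on a 112-day axis, so a spline would need knots within the day, and none are given. What stands is that d0 + 0.75r is exact only under the raw-value, whole-day reading, which is the reading that the listed covariates imply.

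The assay section can also be read as adding draws to the fasting panel, and the schedule table lists hormones without a fasting restriction. That softens the conflict. It does not supply a week 1 visit or name the later weeks.

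Three stronger readings are tempting and are not supported:

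- *That the plan never says when post-meal draws occur.* It does: at baseline, in the first week, then every one to two months. The defect is incomplete timing that does not match the visits.
- *That offsetting effects are to be expected for ghrelin.* The Background says "levels are increased in both obese patients who have lost weight through dietary restriction", and the expected-results text anticipates inhibited ghrelin release. Opposite signs would need more weight loss on high protein and an inhibition that follows the meal. The preliminary isocaloric study found changes of -11.1 and -11.9 lb (p = 0.80), and the expected-results text does not tie the inhibition to meals. If fasting release were also inhibited, the two effects would reinforce each other.
- *That insulin has the same defect.* Insulin is in the fasting panel, and no post-meal insulin series is clearly planned.

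**Conclusion.** The concern holds in this form. Run as listed, the hormone model does not isolate the quantity that Aim 1 asks about. On a test day it estimates d0 + 0.75r, so a fasting shift is indistinguishable from a changed meal response, and an offsetting pair such as 3 and -4 shows as 0 while net incremental AUC differs by -14. This assumes four raw draws on whole days and a rise difference that is constant across 1, 2 and 4 h. It shows what the model cannot separate and does not forecast any hormone's result. No power statement is made, because the documents give no hormone variances or correlations.

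The timing conflict is narrower: there is no week 1 visit, the later series are tied to no named week, and the visit list shows a fasting panel only.

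The point should be corrected, but its reach is limited. Hormone responses are the third-ranked variable in Aim 1, and the primary weight comparison and the sample size do not depend on them.

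**What to change.** 1. Replace the hormone model with one pre-specified postprandial analysis. Either fit nominal meal time (0, 1, 2, 4 h) as a factor with its interactions with diet and visit, allowing for correlation within subject and within subject-visit. Or reduce each test day to one summary, such as incremental AUC or mean rise from fasting, and model that. In both cases test the diet contrast at post-baseline visits, adjusted for baseline.
2. Analyse fasting level as a separate outcome.
3. Reconcile Study Visits with Hormonal and Biochemical Assays so that each post-meal series is tied to a named visit, including the first-week repeat.
4. State the test meal at each series, including baseline. If the baseline meal already differed by arm, the baseline response would not be a clean adjustment variable.

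The cost is some SAP wording, alignment of the schedule and a little more analysis work. The 0, 1, 2 and 4 h draws are already planned.

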Data Analysis: Descriptive statistics (mean, standard deviation, median, inter-quartile range, and frequency distribution) of demographic information and baseline assessments will be generated to characterize the study participants. Patient characteristics and baseline measurements of the three diet groups will be compared using analysis of variance (ANOVA) for continuous variables, and Chi-square test for categorical variables to evaluate the appropriateness of the randomization. If the distribution of the variable is skewed, an appropriate variable transformation will be made before the comparison. Nonparametric methods, such as Kruskal-Wallis one-way analysis of variance, will also be used for comparison.

Primary Endpoint: the primary endpoint is change in body weight, which is calculated as the difference between Day 1 (baseline) and 16 weeks. The primary objective is to compare the weight loss between the high-protein diet and the standard diet. We will use ANOVA to compare the change in weight among the three groups (through contrast), and also use ANCOVA to compare the weight loss among these groups, adjusting for the baseline values and gender. If the primary endpoint is non-normally distributed, the Kruskal-Wallis one-way analysis of variance will be used.

Secondary Endpoints: The secondary endpoints are (1) efficacy variables: nutrition assessments (FFQ, 3DFR, and satiation questionnaire), anthropometric profiles (e.g., waist and hip circumferences), laboratory and biochemical variables (e.g., insulin, lipid levels, HbA1c), body composition (e.g., body fat), liver stiffness, microbiome changes, and level of hormones; (2) safety variables: incidence, severity and duration of adverse events, vital signs, concomitant medications and physical examination results.

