Fecal sampling: Subjects will be provided with kits for home sampling. The subjects will urinate first then defecate into the Fisherbrand Commode Specimen Collection System. Subjects will use a spoon to transfer freshly defecated feces to a Para-Pak stool collection cup prefilled with 95% ethanol to fix the samples, allowing storage at room temperature for up to 2 weeks. The remaining feces will be frozen. This involves removing the cup from the toilet hat, tightly closing the lid, and transferring the cup to a Ziploc bag for storage in the subject's freezer. Frozen samples will be delivered to the VA clinic during scheduled study visits using a Styrofoam box and frozen packs. Subjects who forget to bring samples will be provided with prepaid envelopes to mail their samples to the coordinator. Samples will be stored at -80°C. Ethanol-fixed and fresh frozen samples give comparable metagenomics results to samples stored in preservatives such as RNALater while minimizing subjects' risk of exposure to toxic chemicals^(70,33).

2.1 Kinetic analysis of shifts in microbial composition in obese subjects (BMI 27-40) on a high protein diet compared to an isocaloric normal protein diet.

Experimental protocol: DNA will be extracted from fecal samples collected in ethanol using the MoBio Powersoil kit. Sequencing of the 254 base pair V4 region of 16S ribosomal DNA will be performed as we previously described using the HiSeq 2500 to a depth of >200,000 reads per sample^(71,34). Microbial diversity will be compared between the two dietary groups at each time point using the Chao1 index, Shannon index, and phylogenetic diversity. Significance will be determined using a two-sided t-test. Microbial composition will be compared across all samples using weighted UniFrac (a phylogenetic distance metric) and principal coordinates analysis. Significance of differences in composition will be determined using Adonis.

Microbial abundance will be compared between baseline data for the two groups to confirm that randomization was effective in abolishing a pre-existing microbial difference between the

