two groups. The data for all time points will then be fitted to a multivariate model under a negative binomial distribution using DESeq2 with diet group, time point, interaction between diet and time point, baseline BMI, age, sex, and smoking status as covariates. This model will be compared to a reduced model that does not include the diet:time point interaction⁽⁷⁰⁾. A likelihood ratio test will be used to identify microbes with differential abundance by diet at time points after baseline. Estimates of significance will be adjusted for multiple hypothesis testing⁽⁷¹⁾. OTUs that are differentially abundant on a HPD will be grouped by hierarchical clustering, which we anticipate will highlight distinct kinetic patterns of microbial change.

Expected results/potential pitfalls: We do not anticipate problems with the collection or transportation of fecal samples to our clinical research unit. We predict that *Akkermansia* will significantly increase on a HPD as was seen in our rodent studies. We further predict that most HPD-responsive microbes will have altered abundance within the first 3 to 7 days as has been observed in other dietary studies^(72,73). We estimate a 20% dropout rate based on our high protein meal replacement study, leaving approximately 80 subjects per group. This compares favorably to published studies reporting dietary effects on the microbiome using sample sizes of 10-15^(72,73,74). We anticipate that a HPD will have a similar magnitude of effect as these previously studied diets and hence we expect to have sufficient numbers to detect compositional differences.

2.2 Identification of metagenes affected by a high protein diet.

Experimental protocol: We will assess the functional consequences of altered microbial composition by sequencing the genes carried by intestinal microbes. Shotgun sequencing of DNA extracted from fecal samples will be performed using the HiSeq 3000 with a target depth of 10 GB data per sample, comparable to the 11.7 GB depth used by the Human Microbiome Project for stool samples⁽⁷⁵⁾. Due to the costs of sequencing at this depth, we will only sequence baseline samples and samples from day 112.

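### The mixed models for the continuous secondary variables leave baseline free to differ by diet, which costs precision that the week-0 values already collected could supply

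*Combined protocol and SAP*

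**What the plan says.** All references are to the combined protocol and SAP, section 4.A (Aim 1), Statistical Analysis, unless noted.

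- **Secondary Statistical Analyses, Model 1 (weight over time).** "Covariates include gender, diet group (high-protein and standard), time that the measurement is taken, and an interaction between diet plan and time". The subject-level random effects link the baseline measurement with the follow-up visits, so baseline is one of the repeated outcomes.
- **Same paragraph, continuous efficacy and safety variables.** "Models include the same fixed effects in Model 1, and the subject-level random effects, which account for the correlation between repeated measures at baseline" and the pre-defined later time points. The variables named are the FFQ, 3DFR, satiety, selected laboratory values (HbA1c and insulin are the examples), body fat and vital signs. Neither a baseline covariate nor an equal-baseline constraint is mentioned.
- **Same paragraph, hormones.** A different model: "the covariates in the model include diet group (normal vs. high-protein), time (in days), and smooth-spline function of time by group interaction".
- **Same paragraph, dichotomous and categorical variables.** "generalized linear mixed-effect regressions will be used to model" these, with no covariates listed.
- **Primary Endpoint.** Alongside an ANOVA of change, the plan will "also use ANCOVA to compare the weight loss among these groups, adjusting for the baseline values and gender".
- **Section 4.B (Aim 2.1), microbiome.** Diversity: "Significance will be determined using a two-sided t-test". Abundance at all time points is "fitted to a multivariate model under a negative binomial distribution using DESeq2". Neither is a PROC MIXED model.

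**The concern.** Subjects are randomised 1:1, so the two arms have the same expected mean before the diet starts. A free diet main effect in a model that contains the baseline visit spends information on estimating a difference already known to be zero. The effect at a later visit is then measured against each arm's own observed baseline mean, so baseline is subtracted in full whatever its correlation with follow-up. If the arms differ at baseline by chance by an amount D, the expected value at follow-up differs by rho × D, but the change score removes the whole of D. In that trial it over-corrects by (1 − rho) × D.

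What is at stake is the width of the confidence intervals for the continuous secondary variables. The plan already uses baseline adjustment for weight but does not carry it to these variables.

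**Working it through.** **Inputs from the documents.** Seven visits, at weeks 0, 2, 4, 6, 8, 12 and 16 (Study Visits). Two arms, 1:1 (Statistical Design). About 80 completers per arm (section 4.B, Aim 2.1, expected results). SD of weight loss 10 lb (Sample Size Determination).

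**Assumptions.** rho is not in the documents, so a range is shown. A subject random intercept with equal variance at every visit (sigma² = 1) and complete data are assumed.

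**Step 1. The plan's own figure.** No precision or power is stated for any secondary endpoint. The only power figure is for week-16 weight loss: 165 evaluable, effect size 0.245, 80%. A one-way F test reproduces it as 0.804 with three groups of 55. It gives no base for the secondary models.

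**Step 2. What the planned model estimates.** With categorical time and complete data, the diet-by-week-16 coefficient is the difference between arms in raw change from baseline. Fitted to 40 simulated trials, the mixed-model coefficient and the change-score difference never differed by more than about 1e-14.

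- Planned model: variance = 2(1 − rho) × 2/n. At rho 0.5, n = 80: 1.0 × 0.025 = 0.025.
- Baseline-adjusted: variance = (1 − rho²) × 2/n. At rho 0.5: 0.75 × 0.025 = 0.01875.
- Ratio = (1 − rho²) / [2(1 − rho)] = (1 + rho)/2.

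Simulation with 80 per arm (4,000 runs) gave 0.749 at rho 0.5 and 0.856 at rho 0.7, against 0.75 and 0.85.

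**Step 3. If time is linear.** The plan does not say whether time is categorical or continuous. With a linear term the treatment effect is a slope difference. The exact generalised-least-squares variance was computed for the same seven visits, with and without a common baseline mean. At rho 0.5 it is 0.01677 free and 0.01379 constrained, a ratio of 0.82.

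| rho | ratio, categorical time | CI narrower by (1 − √ratio) | n per arm the planned model needs to match 80 adjusted (160/(1 + rho)) | ratio, linear time |
|---|---|---|---|---|
| 0.3 | 0.65 | 19% | 124 | 0.70 |
| 0.5 | 0.75 | 13% | 107 | 0.82 |
| 0.7 | 0.85 | 8% | 95 | 0.91 |
| 0.9 | 0.95 | 3% | 85 | 0.97 |

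The third and fourth columns apply to categorical time.

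**Step 4. Weight, the one variable for which rho can be approximated.** Section 3.1.B gives baseline weights with ± values. Read them as standard errors, take the four sex-by-group counts in that section (34 and 41 women, 16 and 9 men), and take group A as standard protein; all three are assumptions. Among high-protein women, SD = 4.68 × √34 = 27.3 lb and rho = 1 − 10²/(2 × 27.3²) = 0.93. Across the four subgroups SD is about 24 to 29 lb and rho about 0.92 to 0.94, so 1 − (1 + rho)/2 is 3 to 4%.

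**Step 5. Does deleting the diet main effect cure it?** With categorical time, two arms at seven visits have 14 cell means. Time plus diet-by-time already spans all 14: the design has rank 14 with or without the diet term. Deleting that term refits the same model. Only with continuous time equal to zero at baseline does deletion impose a common baseline mean.

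**The case against.** The strongest reply is that nothing here is invalid. Under randomisation the planned contrast is unbiased with correct type I error, and baseline is used, only not with the best weight. That is right, and it limits the point to efficiency. It does not remove the gain.

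Four further limits stand:

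- A reader might infer that every secondary endpoint is affected. The documents do not support that. The microbiome endpoints use t-tests, Adonis and DESeq2; adverse events have no baseline value; and the covariates of the generalized models are not stated. The hormone model also carries a diet term without a baseline covariate, but its spline form differs and the ratios above do not transfer to it.
- A reader might infer that the planned models simply are change-score analyses. That is exact only for categorical time, complete data and a visit-minus-baseline contrast. The plan does not fix the form of time, and it expects 20% dropout.
- A reader might turn the ratios into a rise from 80% power. No secondary endpoint has a planned power, so that comparison has no base.
- The size depends on a correlation that the documents do not give. For weight the gain is small, and weight already has an ANCOVA "adjusting for the baseline values and gender". That other variables correlate less with their baseline is plausible but cannot be shown from the documents.

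**Conclusion.** The point holds for the continuous variables in the PROC MIXED models and is a free improvement, not a correction of an error. For these variables the plan specifies baseline as an outcome, a free diet effect and no baseline covariate. Using the week-0 value would reduce the variance of the diet effect by 5 to 35% with categorical time, or by about 3 to 30% with linear time, for rho from 0.9 down to 0.3. These figures rest on an assumed rho, a random-intercept covariance, equal variances over time and complete data. For weight the reduction is probably 3 to 4%, if the preliminary ± values are standard errors. Neither bias nor an inflated type I error follows from the planned specification.

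**What to change.** In Secondary Statistical Analyses, for each continuous variable with a week-0 value, use one of the following:

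1. **Baseline as covariate (simplest).** Model the post-baseline visits only, with the subject's own week-0 value, gender, diet, time and diet-by-time as fixed effects.
2. **Common baseline mean.** Keep week 0 among the outcomes and code both arms as control at that visit, so that diet enters only from the first post-baseline visit. The plan should then confirm that the week-0 values are taken before the diet starts. With categorical time, removing the diet main effect alone does not achieve this.

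In either case, state whether time is categorical or continuous, and name the contrast that is the treatment effect (for example, the diet difference at week 16).

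The cost is a few lines of SAP text and a small change to the PROC MIXED code before the data are analysed. No additional visits, subjects or measurements are needed, because week-0 assessments of these variables are already scheduled.
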